5.3 Lifestyle Considerations

5.3.1 Meals and Dietary Restrictions

5.3.1.1 Diet Restrictions

Fasting requirements for study procedures, such as but not limited to laboratory safety evaluations are specified in Section 8.

In each treatment panel (except for Panel D, described separately below), participants will fast from all food and drinks, except water, for at least 10 hours prior to study drug administration. Participants will fast from all food and drinks except water between study drug administration and the first scheduled meal. Meals and snack(s) will be provided by the investigator at time points indicated in the SoA. Participants will fast from all food and drinks except water between meals and snacks. The caloric content and composition of meals will be the same in each treatment panel. After the 24-hour post-dose procedures have been completed, subsequent meals and snacks will be unrestricted in caloric content, composition and timing.

In Panel D, following an overnight fast of at least 10 hours, breakfast will be provided to participants approximately 30 minutes prior to study drug administration. Breakfast should be consumed in its entirety within approximately 20 minutes. The start and stop time of the breakfast will be recorded. Within approximately 10 minutes after consuming the breakfast, subjects will be administered trial drug as indicated in Section 8.1.8, and participants will fast from all food and drink, except water, for at least 4 hours following dosing. In Panel D, participants will consume a high-fat, moderate-fat, or low-fat breakfast (to be determined following the review of emerging safety and PK data from the ongoing studies, Protocols 001 and 002). The contents of the breakfasts are listed in [Table 8](#), [Table 9](#), and [Table 9](#).

Table 7 Contents of the Standard, High-Fat Breakfast

2 fried or scrambled eggs
2 strips bacon
2 slices toast with 2 pats of butter
4 oz (113 g) hash browns (fried potato)
240 mL whole milk

The nutritional content of the high-fat breakfast is as follows:

Total fat = 55.6 g

Total carbohydrates = 55 g

Total protein = 31.1 g

Total calories = 500.4 in fat, 220 in carbohydrates, and 124.4 in protein.

Table 8 Contents of the Standard, Moderate-Fat Breakfast

Brown bread (70 g)
Butter (15 g)
Cheese (40 g)
Jam (15 g)
240 mL Whole milk

The nutritional content of the moderate-fat breakfast is as follows:

Total fat = 34 g (31% of calories)

Total carbohydrates = 53 g (48% of calories)

Total protein = 22 g (20% of calories)

Total calories = 619 Kcalories

Table 9 Contents of the Standard, Low-Fat Breakfast

2 small bread rolls (60 g)
Light cream cheese (65 g)
Fat free milk (160 mL)

The nutritional content of the low-fat breakfast is as follows:

Total fat = 9 g (8% of calories)

Total carbohydrates = 43 g (37% of calories)

Total protein = 15 g (13% of calories)

Total calories = 312 Kcalories

The exact meal contents may be substituted with agreement between Sponsor and Investigator and must be documented in an administrative letter. The specific nutritional content of the breakfast may be modified during the study based on newly available data.

Instructions on whether to take MK-8558 with or without food and/or drink may be modified during the study based on newly available data.

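### Do the wrong calorie percentages printed for two of the Panel D breakfasts call for a change to the plan?

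*Combined protocol and SAP*

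**What the plan says.** Section 5.3.1.1 (Diet Restrictions) gives foods and nutritional content for the three candidate breakfasts.

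- **High-fat (Table 7):** 55.6 g fat, 55 g carbohydrate and 31.1 g protein, with 500.4, 220 and 124.4 kcal from each. No percentages are given.
- **Moderate-fat (Table 8):** "Total fat = 34 g (31% of calories", "Total carbohydrates = 53 g (48% of calories", "Total protein = 22 g (20% of calories", and "Total calories = 619 Kcalories".
- **Low-fat (Table 9):** "Total fat = 9 g (8% of calories", "Total carbohydrates = 43 g (37% of calories", "Total protein = 15 g (13% of calories", and "Total calories = 312 Kcalories".

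One of the three is served before dosing in Panel D only. Sections 1.3, 4.1 and 5.3.1.1 say that the category is picked after review of emerging safety and PK data. Section 4.1 adds that the choice is announced in a memo before dosing. Table 1 in Section 1.2 marks Panel D as optional. Section 5.3.1.1 lets the sponsor and investigator agree on substitute contents, recorded in an administrative letter.

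**The concern.** Fat content is the one attribute that separates the three meals, and here the printed fat shares are far from what the printed grams imply. The low-fat shares leave 42% of the calories unassigned, although the three macronutrients already account for all of the stated energy.

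If the percentages were taken at face value, the moderate-fat meal would look much leaner than it is. Its fat share works out close to that of the high-fat meal, which is 500.4 / 844.8 = 59%. A report that copied the labels would misdescribe the condition under which Panel D's exposure and viral-load data were obtained. A substitute meal matched to the percentages would differ from the one listed.

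**Working it through.** **Inputs.** Grams, percentages and total kcal are those in Section 5.3.1.1, set out above.

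**Conversion factors.** Table 7 supplies them: 500.4 / 55.6 = 9 kcal per g of fat, 220 / 55 = 4 for carbohydrate, 124.4 / 31.1 = 4 for protein.

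**Stated totals.** Total kcal = 9 × fat + 4 × carbohydrate + 4 × protein.

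- Moderate-fat: 9 × 34 + 4 × 53 + 4 × 22 = 306 + 212 + 88 = 606, against 619 stated (13 kcal, or 2.1%, lower).
- Low-fat: 9 × 9 + 4 × 43 + 4 × 15 = 81 + 172 + 60 = 313, against 312 stated (1 kcal, or 0.3%, higher).

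The totals reproduce closely. The grams are printed to the nearest whole number, so rounding alone moves each sum by up to 0.5 × (9 + 4 + 4) = 8.5 kcal. That covers the low-fat gap and most of the moderate-fat one.

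**Shares of calories.** Share = kcal from the component / sum of components.

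| Meal | Component | From grams | Printed |
|---|---|---|---|
| Moderate-fat | Fat | 306 / 606 = 50.5% | 31% |
| | Carbohydrate | 212 / 606 = 35.0% | 48% |
| | Protein | 88 / 606 = 14.5% | 20% |
| Low-fat | Fat | 81 / 313 = 25.9% | 8% |
| | Carbohydrate | 172 / 313 = 55.0% | 37% |
| | Protein | 60 / 313 = 19.2% | 13% |

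Dividing by the stated 619 kcal instead gives 49.4 / 34.2 / 14.2% for the moderate-fat meal, which does not help. The printed shares add to 99% and 58%.

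**Could another calorie total explain them?** Allow each printed percentage ±0.5 point and solve for the base.

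- Moderate-fat: the fat line needs 306 / 0.315 to 306 / 0.305 = 971 to 1003 kcal; the carbohydrate line needs 212 / 0.485 to 212 / 0.475 = 437 to 446 kcal.
- Low-fat: the fat line needs 81 / 0.085 to 81 / 0.075 = 953 to 1080 kcal; the carbohydrate line needs 172 / 0.375 to 172 / 0.365 = 459 to 471 kcal.

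The ranges do not overlap in either meal, so no single calorie total produces the printed set.

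**Are they shares of weight?** The moderate-fat macronutrients weigh 34 + 53 + 22 = 109 g, and 34 / 109, 53 / 109 and 22 / 109 are 31.2, 48.6 and 20.2%. That is close to the printed 31, 48 and 20%, though 48.6 would round to 49. The low-fat macronutrients weigh 9 + 43 + 15 = 67 g, with weight shares of 13.4, 64.2 and 22.4%, which are not the printed values. The low-fat percentages would need a base of about 115 to 118 g, which the documents do not give. Mislabelled weight shares are therefore a plausible source for Table 8; the source for Table 9 cannot be identified.

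**Where the percentages are used.** The order of the meals by grams of fat is 55.6 > 34 > 9, as their names say. The visible endpoints (Section 9.4), populations (9.5) and methods (9.6), and the review before each new panel (6.6), make no use of meal percentages.

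**The case for a change.** The strongest case for acting is the substitution clause. A substitute built to the printed percentages at the printed energy would carry 0.31 × 619 / 9 = 21.3 g of fat instead of 34 g, or 0.08 × 312 / 9 = 2.8 g instead of 9 g. The correction would cost only six figures.

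The arithmetic behind this stands in full. Nothing in the text suggests redaction or a conversion fault as the cause, and fat content is what the choice of meal turns on. The harm, however, needs someone to work from the percentage and ignore the foods, grams and kcal printed beside it. For the low-fat meal, anyone using the percentages would see at once that they do not add to 100. A substitution also needs agreement between sponsor and investigator and a written record. What remains is a descriptive error that could mislead a careless reader.

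**Conclusion.** The mismatch is genuine: fat is about 50% of calories in the moderate-fat meal, not 31%, and about 26% in the low-fat meal, not 8%. It is a clerical slip and calls for no change to the plan. The meal specification rests on foods, grams and total energy, which agree within about 2%, so the stated totals need no correction either. The choice among meals is by category, and the panel that would use one is optional.

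This rests on two assumptions. First, that the grams are right: their agreement with the stated kcal favours them, but only the sponsor's source meal data can settle which figures were intended. Second, that the redacted parts of the statistical section make no use of the percentages; nothing visible suggests that they do. A study report describing Panel D can give grams and kcal and leave the percentages out, unless the sponsor has by then checked them against the source data.

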5.3.1.2 Fruit Juice Restrictions

Participants will refrain from the consumption of grapefruit juice, grapefruits, and grapefruit products beginning approximately 2 weeks prior to administration of the initial dose of study drug, throughout the study, and until the post-study visit.

Participants also will refrain from the consumption of all fruit juices 24 hours prior to and after study drug administration. On all other days during the study, consumption of fruits and fruit juices (except for grapefruit, grapefruit juices, and grapefruit products) is allowed.

5.3.2 Caffeine, Alcohol, and Tobacco Restrictions

5.3.2.1 Caffeine Restrictions

Participants will refrain from consumption of caffeinated beverages or xanthine-containing products from 12 hours prior to the pre-study and post-study visits and from 12 hours prior to and after study drug administration. At all other times, caffeinated beverages or xanthine-containing products will be limited to no more than 6 units per day amounts (1 unit = 120 mg of caffeine).

5.3.2.2 Alcohol Restrictions

Participants will refrain from consumption of alcohol 24 hours prior to the pre-study and post-study visits and from 24 hours prior to and after study drug administration. At all other times, alcohol consumption is limited to no more than approximately 3 alcoholic beverages or equivalent (1 glass is approximately equivalent to: beer [354 mL/12 ounces], wine [118 mL/4 ounces], or distilled spirits [29.5 mL/1 ounce]) per day.

5.3.2.3 Tobacco Restrictions

Smoking (and/or the use of nicotine/nicotine-containing products) should be restricted to ≤ 10 cigarettes per day and participants will be required to follow the smoking restrictions defined by the CRU while on site.

5.3.3 Activity Restrictions

Participants will avoid unaccustomed strenuous physical activity (e.g., weight lifting, running, bicycling, heavy gardening, moving heavy objects, etc.) from the pre-study (screening) visit until administration of the initial dose of study drug, throughout the study, and until the post-study visit. Participants will be asked to rest semi-recumbent for 4 hours

post-dose, except to stand for the measurement of orthostatic vital signs (if needed) or any other trial related procedure.

5.4 Screen Failures

Screen failures are defined as participants who consent to participate in the clinical study but are not subsequently entered in the study. A minimal set of screen failure information may be included, as outlined in the electronic case report forms (eCRF) entry guidelines. Minimal information may include demography, screen failure details, eligibility criteria, and any AEs or SAEs meeting reporting requirements.

5.5 Participant Replacement Strategy

If a participant discontinues from study intervention or withdraws from the study, a replacement participant may be enrolled if deemed appropriate by the investigator and Sponsor. The replacement participant will generally receive the same intervention or intervention sequence (as appropriate) as the participant being replaced. The replacement participant will be assigned a unique treatment/randomization number. The study site should contact the Sponsor for the replacement participant's treatment/randomization number.

6 STUDY INTERVENTION

Study intervention is defined as any investigational intervention(s), marketed product(s), placebo, or medical device(s) intended to be administered to a study participant according to the study protocol.

Clinical supplies [study interventions (MK-8558) provided by the Sponsor] will be packaged to support enrollment and replacement participants as required. When a replacement participant is required, the Sponsor or designee needs to be contacted prior to dosing the replacement supplies. Clinical supplies will be affixed with a clinical label in accordance with regulatory requirements.

6.1 Study Intervention(s) Administered

The study interventions to be used in this study are outlined in [Table 10](#).

Table 10 Study Interventions

Arm Name	Arm Type	Intervention Name	Type	Dose Formulation	Unit Dose Strength(s)	Dosage Level(s)	Route of Administration	Regimen/Treatment Period	Use	IMP/NIMP	Sourcing
Panel A	Experimental	MK-8558	Drug	Tablet	10 mg 100 mg	400 mg	Oral	Single Dose	Experimental	IMP	Provided centrally by the Sponsor
Panel B	Experimental	MK-8558	Drug	Tablet	10 mg 100 mg	≤900 mg	Oral	Single Dose	Experimental	IMP	Provided centrally by the Sponsor
Panel C	Experimental	MK-8558	Drug	Tablet	10 mg 100 mg	≤1600 mg	Oral	Single Dose	Experimental	IMP	Provided centrally by the Sponsor
Panel D	Experimental	MK-8558	Drug	Tablet	10 mg 100 mg	≤1600 mg	Oral	Single Dose	Experimental	IMP	Provided centrally by the Sponsor
Definition Investigational Medicinal Product (IMP) and Non-Investigational Medicinal Product (NIMP) is based on guidance issued by the European Commission. Regional and/or Country differences of the definition of IMP/NIMP may exist. In these circumstances, local legislation is followed.											

All supplies indicated in Table 10 will be provided per the "Sourcing" column depending upon local country operational requirements. If local sourcing, every attempt should be made to source these supplies from a single lot/batch number where possible (e.g., not applicable in the case where multiple lots or batches may be required due to the length of the study, etc).

Refer to Section 8.1.8 for details regarding administration of the study intervention.

6.2 Preparation/Handling/Storage/Accountability

6.2.1 Dose Preparation

There are no specific calculations or evaluations required to be performed in order to administer the proper dose to each participant. The rationale for selection of doses to be used in this study is provided in Section 4.3.

6.2.2 Handling, Storage, and Accountability

The investigator or designee must confirm appropriate temperature conditions have been maintained during transit for all study intervention received, and any discrepancies are reported and resolved before use of the study intervention.

Only participants enrolled in the study may receive study intervention, and only authorized site staff may supply or administer study intervention. All study interventions must be stored in a secure, environmentally controlled, and monitored (manual or automated) area in accordance with the labeled storage conditions with access limited to the investigator and authorized site staff.

The investigator, institution, or the head of the medical institution (where applicable) is responsible for study intervention accountability, reconciliation, and record maintenance (ie, receipt, reconciliation, and final disposition records).

For all study sites, the local country Sponsor personnel or designee will provide appropriate documentation that must be completed for drug accountability and return, or local discard and destruction if appropriate. Where local discard and destruction is appropriate, the investigator is responsible for ensuring that a local discard/destruction procedure is documented.

The study site is responsible for recording the lot number, manufacturer, and expiry date for any locally purchased product (if applicable) as per local guidelines unless otherwise instructed by the Sponsor.

The investigator shall take responsibility for and shall take all steps to maintain appropriate records and ensure appropriate supply, storage, handling, distribution, and usage of study interventions in accordance with the protocol and any applicable laws and regulations.

6.3 Measures to Minimize Bias: Randomization and Blinding

6.3.1 Intervention Assignment

Participants in this study will be assigned to panel and treatment according to an allocation schedule. A sample allocation schedule is shown in [Table 11](#).

Table 11 Sample Allocation Schedule

Panel	N	Dose of MK-8558 ^a			
A	6	400 mg			
B ^b	6		≤900 mg		
C ^b	6			≤1600 mg	
D ^b	6				≤1600 mg with food

a. Doses may be adjusted downward following review of safety and viral load data from preceding panels.
b. The doses to be administered in Panels B, C and D will be based on the results of safety and viral load data out to at least Day 8 in Panels A, B and C, respectively.

6.3.2 Stratification

No stratification based on age, sex, or other characteristics will be used in this study.

6.3.3 Blinding

This is an open-label study; therefore, the Sponsor, investigator, and participant will know the intervention administered.

6.4 Study Intervention Compliance

Interruptions from the protocol-specified treatment plan require consultation between the investigator and the Sponsor and written documentation of the collaborative decision on participant management.

6.5 Concomitant Therapy

If a participant does not discontinue all prior medications within 14 days or 5 half-lives of the first dose of study intervention, he/she may be included in the study if the investigator can rationalize that the specific use of a prior medication is not clinically relevant within the context of the study.

Concurrent use of any prescription or nonprescription medication, or concurrent vaccination, during the ongoing study (i.e., after randomization or intervention allocation) must first be discussed between the investigator and Sponsor prior to administration, unless appropriate medical care necessitates that therapy or vaccination should begin before the investigator and

Sponsor can consult. The participant will be allowed to continue in the study if both the Sponsor and the investigator agree.

Paracetamol/acetaminophen (maximum 4 grams in 24 hours) or ibuprofen (maximum 600 mg in 24 hours) may be used for minor ailments without prior consultation with the Sponsor.

[REDACTED]

[REDACTED]

6.5.1 Rescue Medications and Supportive Care

No rescue or supportive medications are specified for use in this study.

6.6 Dose Modification (Escalation/Titration/Other)

Prior to proceeding to the next panel, the following data from at least 4 evaluable subjects from the previous dosing panel will be reviewed:

- key safety data including vital signs, 12-lead ECGs, laboratory safety tests, and AEs from the previous dose levels up to at least 168 hours post dose
- viral dynamic data (out to 168 hours post-dose)

Before proceeding to Panel B, PK data from Panel A (a minimum of 4 evaluable subjects) will be reviewed to compare PK from HIV-infected participants with PK observed in healthy participants in Protocol 001, to ensure that doses selected for Panel B are appropriate from both efficacy and safety standpoints.

In addition, safety, tolerability, and PK data from doses up to 1600 mg (including a food-effect assessment) from the ongoing Protocol 001 have been reviewed and support the proposed dosing for Protocol 002.

Based on the review of data (specified above), modifications to planned dosing may be implemented, including:

- administration to a subsequent panel the same dose level to further evaluate that particular level;
- administration of a lower dose of the study treatment;
- administration of the same or lower dose as a divided dose; or
- administration of the same or a lower dose with or without food.

Or, dosing may be stopped. Participant discontinuation criteria are outlined in Section 7.

6.6.1 Stopping Rules

Enrollment of the trial will be halted in the following circumstances:

1. One participant (cumulatively) reports a serious AE with a potential causal relationship to the study drug or two (2) participants per panel report severe AEs with a potential causal relationship to study drug.
2. Three (3) or more of the enrolled participants (cumulatively) experience the same AE requiring withdrawal from the study, or the same severe AE assessed as having a potential causal relationship to study drug.
3. Two (2) participants (cumulatively) experience severe but not life threatening AEs or severe clinically significant laboratory abnormalities that are similar in nature.
4. One (1) serious AE/laboratory abnormality (cumulatively) is reported that is life threatening, results in persistent or significant disability/incapacity, results in or prolongs an existing inpatient hospitalization, or is another important medical event OR participant death thought to be potentially related to the investigational product.
5. Two (2) or more of the enrolled participants experience confirmed QTcF > 500 ms or QTcF change from baseline > 60 ms in a given panel with a potential causal relationship to study

If one of the above circumstances occurs, enrollment and dosing will be halted, and an internal safety review will be conducted prior to making a decision about terminating the study. The safety of participants will be assessed on an ongoing basis, and while conditions that could warrant early trial termination are not limited to those noted above, these criteria are meant to pre-specify circumstances under which the trial may be terminated early. In the event that the trial is interrupted or safety data suggest that the benefit-to-risk assessment has been meaningfully altered and must be reassessed, the Regulatory Authority will be notified.

6.7 Intervention After the End of the Study

There is no study-specified intervention following the end of the study.

6.8 Clinical Supplies Disclosure

This study is open-label; therefore, the participant, the study site personnel, the Sponsor, and/or designee are not blinded. Study intervention (name, strength, or potency) is included in the label text; random code/disclosure envelopes or lists are not provided.

7 DISCONTINUATION OF STUDY INTERVENTION AND PARTICIPANT WITHDRAWAL

7.1 Discontinuation of Study Intervention

Discontinuation of study intervention does not represent withdrawal from the study.

As certain data on clinical events beyond study intervention discontinuation may be important to the study, they must be collected through the participant's last scheduled follow-up, even if the participant has discontinued study intervention. Therefore, all participants who discontinue study intervention prior to completion of the protocol-specified treatment regimen will still continue to participate in the study as specified in Section 1.3 and Section or if available, a protocol clarification letter.

Participants may discontinue study intervention at any time for any reason or be discontinued from the study intervention at the discretion of the investigator should any untoward effect occur. In addition, a participant may be discontinued from study intervention by the investigator or the Sponsor if study intervention is inappropriate, the study plan is violated, or for administrative and/or other safety reasons. Specific details regarding procedures to be performed at study intervention discontinuation are provided in Sections 8.1.9 and 8.10.3.

A participant must be discontinued from study intervention but continue to be monitored in the study for any of the following reasons:

1. The participant requests to discontinue study intervention.
 - The participant has a medical condition or personal circumstance which, in the opinion of the investigator and/or Sponsor, placed the participant at unnecessary risk from continued participation in the study.
 - The participant has a positive urine drug screen (excluding cannabis) confirmed upon recheck at any time during the course of the study.

For participants who are discontinued from study intervention all applicable discontinuation activities will be performed according to Section 8.1.9, or if available, a protocol clarification letter.

Discontinuation from study intervention is “permanent.” Once a participant is discontinued, he/she shall not be allowed to restart study intervention.

